The wound area to be followed in the study will be between 200cm² and 640cm². One ReCell kit is intended to treat up to 320cm² (which will cover half of the total “maximum” 640cm² wound area), allowing for comparison with a similar size control area of up to 320cm² that is treated according to the standard of care.

In all cases, the ReCell region may be up to 320cm² in size, the upper limit of application area for one ReCell kit, with a similarly sized control region. If the wound is larger than the combined control and ReCell regions (over 640 cm²), areas outside the study regions will be designated non-study areas and treated according to the standard of care. Additionally, areas with incomplete granulation, defined as a contiguous vascularized granulation layer at the INTEGRA™ MBWM application site, will be excluded from the study wound area.

The same primary and secondary dressings will be used on ReCell-treated areas, control areas and donor sites. Once the wounds are determined to be healed, standard local clinical practice will be followed.

In order to evaluate improvements associated with use of ReCell, within-subject comparisons across a battery of measurements and evaluations will be made. These measurements are divided into three categories:

- Safety and tolerability measures
- Preliminary effectiveness (acute healing phase)
- Long-term effectiveness

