Subjects will be anesthetized and the wound will be prepared according to hospital standard of care practices. It is anticipated that the total surgical time will be up to 3 hours. The operative procedure will be performed by the PI and/or the Co-PI in the operating room at WRNMMC. The INTEGRA™ MBWM treated wound will be sectioned into two **similarly sized** study regions up to 320cm² each, the upper limit of application area for one ReCell kit. The surgeon will label these two regions “A” and “B” with a surgical pen. A pre-generated randomization envelope will then be opened to determine which area will be the control area and which area will be treated with ReCell. Any wound area outside the study regions will be treated according to standard of care.

In this study, serial histology assessments of the wound site will be made. Baseline punch biopsies of 3 mm diameter tissue samples from the INTEGRA™ MBWM treated wound site and adjacent normal skin will be obtained in the operating room prior to start of the surgical procedure. This baseline histological analysis will examine the vasculogenesis and cytology of the regenerate before ReCell treatment. The biopsy procedure will be recorded in the eCRF.

A digital photograph will be taken of the control and ReCell sites (“A” region and “B” region) and noted on the eCRF. Next, the wound bed will be gently scrubbed and “prepared” then the thin silicone layer is removed, the wound bed will be prepped and prepared again for receipt of proposed STSG or STSG in conjunction with ReCell regenerative skin treatment system.

Harvesting of autograft will be the same thickness for both control and investigational site; at a depth of 0.012 inch to 0.016 inch which is alignment with standard of care practice. Donor tissue for the STSG for the ReCell treatment area may be harvested from the same area as for the control STSG or separate area. To assess healing of the donor sites for ReCell, the site has to be at a discrete location, but can be collocated, i.e. same thigh, but different area.

A digital photograph will be taken of donor sites following tissue removal and will be noted in the eCRF. These and all subsequent photographs at each study visit will be taken in ambient light, with a consistent background and distance between camera and subject.

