Appendix H - Data Management Plan, including Statistical Management Plan

Appendix I - Clinical Monitoring Plan

Appendix J - Schematic

Appendix K - Budget

Appendix L – Sample electronic Case Report Forms (eCRF)

Procedure	Screening/ Pre-Treatment	OR	Assessments for Safety Tolerability and Preliminary Effectiveness					Assessments for Safety, Aesthetic, & Functional Outcomes	
			Week 1	Week 2	Week 3	Week 4	Week 6	Week 12	Week 24
Visit Window Interval	-30 Days		±3 days	±2 days	±2 days	±2 days	±2 days	±14 days	±14 days
Informed Consent/Enrollment	X								
Medical History ^a	X								
Demographics ^b	X								
Physical Examination	X								
Vital Signs ^c	X		X	X	X	X	X	X	X
Injury Assessment of area treated with INTEGRA TM MBWM ^d	X								
Pain and Pruritus (baseline eval)	X								
Hematology/Chemistry ^e	X		X						
Radiographic Imaging ^f	X								X
Verification of Eligibility Criteria ^g	X								
Randomization ^h		X							
Histology ⁱ		X		X		X		X	
Digital Photography ^j		X	X	X	X	X	X	X	X
Donor Site Tissue Harvesting ^k		X							
Application of Investigational Product (ReCell Procedure)		X							
Wound & Donor Site Healing Assessments ^l			X	X	X	X	X	X	
POSAS ^m			X	X	X	X	X	X	X

Vancouver Scar Scale (VSS)								X	X
Functional Outcome Rating								X	X
Patient Satisfaction								X	X
Concomitant Medicationsⁿ	X		X	X	X	X	X	X	X
Adverse Events^o	X	X	X	X	X	X	X	X	X

- a) Current medication use and allergies
- b) Date of birth, gender, race/ethnicity
- c) Oral temperature, heart rate, respiration rate and blood pressure
- d) Assessment to determine if traumatic wound is fully engrafted as indicated by formation of a viable granulation layer
- e) Complete blood count (CBC) with differential panel coagulation studies to include prothrombin time (PT) and international normalized ratio (INR) and comprehensive metabolic panel (CMP)
- f) Radiographic imaging (anterior/posterior and lateral films) for assessment of heterotopic ossification (presence/absence) pre-treatment/baseline if not previously obtained within 30 days of study enrollment and at Week 24 post-treatment
- g) Verification of eligibility will be performed at Screening and Re-verification of eligibility just prior to picking up investigational device from pharmacy
- h) Wound site will be labeled as “A” region and “B” region PRIOR to opening randomization envelope

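### The randomization envelope is opened before the silicone is removed and the bed finally prepared, so both regions are prepared by an operator from whom the allocation is not concealed

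*Combined protocol and SAP*

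**What the plan says.** Section 5.5.4, under Surgical Procedure and Methods, begins with a general step: "Subjects will be anesthetized and the wound will be prepared according to hospital standard of care practices". The surgeon then sections the wound, marks the regions A and B with a surgical pen, and "A pre-generated randomization envelope will then be opened to determine which area will be the control area".

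Two paragraphs later, "A digital photograph will be taken of the control and ReCell sites". Bed preparation follows: "Next, the wound bed will be gently scrubbed", "then the thin silicone layer is removed, the wound bed will be prepped and prepared again for receipt of proposed STSG". Donor harvest, meshing, graft placement and the ReCell procedure are described after that.

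The envelope also appears in Section 5.1, in the Randomization paragraph of Section 5.7.3, and in note h to the schedule of procedures in the appendices. Note h requires labelling "PRIOR to opening randomization envelope". All three put labelling first. None links the opening to bed preparation.

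The operator is the PI and/or the Co-PI. The only parties described as blinded are the subject (5.1, 5.5.4) and the two independent scar observers (5.5.4).

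Section 5.1 contains the sentence beginning "Additionally, areas with incomplete granulation, defined as a contiguous vascularized granulation layer", which takes areas of incomplete granulation out of the study wound area. A note to the inclusion criteria in 5.4 repeats the exclusion.

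**The concern.** In a within-wound design the region is the experimental unit. The comparison is fair only if the two regions are handled alike until the treatments diverge. Scrubbing, removing the silicone and preparing the bed again leave room for judgement, and they are done after the allocation is out.

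The plan itself treats this work as relevant to outcome: the risk table in Section 6.2 lists wound-site preparation among the mitigations for infection and for failure of graft take. If one region were prepared more thoroughly, or lost a doubtful patch when the silicone came off, the difference would appear as a treatment effect on graft loss, infection or delayed healing. Section 5.7.1 lists all three as primary outcomes.

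**Working it through.** No arithmetic bears on the sequence, and the plan gives no figure for this point. The check sets the texts side by side.

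1. **Order of steps in 5.5.4.**
   - General wound preparation.
   - Sectioning and A/B labelling.
   - Envelope opened.
   - Photograph of the two sites.
   - Scrub and first bed preparation.
   - Silicone removed and bed prepared again.
   - Donor harvest, meshing, placement, cell suspension.

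   The words *then* (envelope) and *next* (scrub) carry the order. At the photograph the sites already have treatment names.

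2. **Is the section chronological throughout?** No. The baseline biopsies are described after the envelope but are timed before the surgical procedure starts. They are left out of the list above. The order of envelope, photograph and bed preparation does not depend on them.

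3. **Does another section delay the envelope?** No. Sections 5.1 and 5.7.3 and note h to the schedule fix only labelling before opening.

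4. **Who knows the allocation during bed preparation?** The documents do not say who opens the envelope. No step withholds the result from the operator, who needs it to place the grafts. That the operator knows it is an inference, but a fair one.

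5. **Could a boundary change at this stage?** Engraftment is inspected at screening, up to 30 days before treatment. Eligibility is re-verified on the day of surgery before the kit is obtained. Both come before the silicone is removed. No text fixes the boundaries at labelling, and none describes changing them later.

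6. **Does anything downstream offset unequal preparation?** Atypical healing, graft loss and infection are assessed at the post-treatment visits by an investigator, with no blinding stated. The scar observers are blinded, but they do not rate these outcomes.

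7. **How late could the envelope be opened?** No bed-preparation step is described as differing by treatment, so preparation does not need the allocation. Harvest can need it, for three reasons:
   - The regions are only similar in size and the mesh ratios differ (1:1.5 and 1:5), so the amount of graft required depends on which region gets which mesh.
   - The ReCell biopsy is sized to its region. At the 1:80 expansion in 5.6.2, a 320 cm² region needs 320 / 80 = 4 cm² of skin, and a smaller region needs less.
   - The ReCell donor site is matched to the area to be treated.

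   The window is therefore after bed preparation and before any harvest. This fits the order in which 5.5.4 already describes those two steps.

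**The case against.** The best case for the plan is that the regions are defined and labelled before anyone sees the assignment, and that each subject receives both treatments, so neither enrolment nor the initial division can be steered. Some preparation also precedes the envelope. Bed preparation is described for the wound as a whole, with no step that differs by region. The operator must learn the allocation shortly afterwards in any case, and the later assessment by an investigator with no stated blinding is a larger route to bias that reordering leaves untouched. Section 5.7.2 adds that the study evaluates no formal hypotheses.

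Most of this stands, and it limits what can be claimed. A reader might infer more in four ways:

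- *Allocation concealment is lost.* It is not lost for the A/B division. The exposure is confined to the later preparation and to any boundary change made then.
- *Nothing is prepared before the envelope.* A general preparation is. The exposed steps are the scrub, the silicone removal and the second preparation.
- *Boundaries will be redrawn, or one side prepared better.* The documents describe neither. They only fail to rule them out.
- *The bias is about 5 percentage points.* That figure is 1/20 = 0.05, the weight of any one subject among 20. It does not estimate this effect.

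The feasibility label does not dispose of the point. The regions are randomized so that they can be compared, Section 3 predicts non-inferiority, 5.7.3 plans a treatment-by-time test, and 5.7.2 says the results may shape a pivotal trial.

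**Conclusion.** The point holds in a limited form. Followed as written, the plan exposes the scrub, silicone removal and second bed preparation of both regions to a known allocation, in each of the 20 planned subjects. It also leaves open a boundary change at that stage. This is an opportunity for performance bias in primary outcomes that have no stated blinded assessment. The documents contain no evidence that the regions would be treated differently, and the size of any bias cannot be computed from them.

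The conclusion rests on two readings: that the sequence words in 5.5.4 mean what they say, and that the operator learns the allocation when the envelope is opened. The change is advisable because it is simple. The defect does not by itself invalidate the comparison.

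**What to change.** In Section 5.5.4, state that the envelope is opened only after both regions have had the silicone removed and the bed prepared, and after final boundaries and areas have been recorded, but before any STSG or ReCell donor harvest. Record the opening time on the eCRF. Align Section 5.1, the Randomization paragraph in 5.7.3 and note h to the schedule. Note h already accepts the principle that the regions are settled before the allocation is revealed; this extends it to bed preparation.

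The cost is a minor reordering of operative steps and a few added eCRF entries. Sample size, alpha and power do not change. The benefit is limited to bed preparation and boundaries, since the operator must know the allocation from harvest onward. Investigator assessment of healing without stated blinding needs separate attention.

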Based on preclinical and early clinical results, the short-term benefits of this study will include potential viable and readily available regeneration of necessary autologous skin to place on a dermal regenerate in massive soft tissue injuries. This clinical model would be the first to potentially show the benefit of such treatments in traumatic wounds, outside of burn patients. It would also have immense benefits - both for those military healthcare beneficiaries suffering from soft tissue injuries as well as traumatic civilian injuries that likewise pose significant issues with available autologous skin coverage (e.g. necrotizing fasciitis, motor vehicle accidents or other trauma with associated soft tissue avulsion injuries, etc.). Important data on the mechanism of action, refinements of technique, expansion of the device and technique to future applications, and most importantly, technology transfer throughout WRNMMC, associated military treatment facilities (MTF), and civilian or academic centers is of great interest.

We expect all ReCell treated and control areas of the wounds to heal adequately. However, we hypothesize areas treated with ReCell will re-epithelialize more quickly than control areas, which has the potential to reduce the risk of infection and scarring in ReCell treated areas compared to control areas. Healing will be defined as: 95% or greater re-epithelialization has occurred at area treated by Week 6 post-treatment.

4.4 Human Subjects Justification.

The proposed prospective, non-randomized, within-patient controlled feasibility study will enroll 20 military healthcare beneficiaries, both male and female, currently

receiving treatment for a traumatic wound injury at WRNMMC. The goal of this study is to evaluate the safety, tolerability, preliminary and long-term effectiveness of the ReCell device for re-epithelialization of full-thickness wounds treated with INTEGRA™ MBWM.

Data collected in the completion of the proposed study will support or refute the hypothesis that the use of the ReCell device over a widened STSG mesh in combination with INTEGRA™ MBWM will improve upon the current standard of care for treating full-thickness wounds within the traumatic injury population. We believe that ReCell will promote improved healing within the interstices of finely meshed STSG, thus improving durability among STSG gaps that are potential points of failure during later physical activity.

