5. PLAN

5.1 Study Design

This is a prospective, single-center, randomized within-patient controlled feasibility study to evaluate safety, tolerability, preliminary and long-term effectiveness of the ReCell device when used in combination with STSG mesh for healing of full-thickness wounds previously treated successfully with INTEGRA™ MBWM. Due to the nature of the study, only patients whose wounds have been treated with INTEGRA MBWM as part of their standard of care will qualify for study participation. The local standard of care is considered the application of INTEGRA MBWM after the wound is amenable. Amenable being no evidence of evolving necrosis, clean and devoid of infection. The INTEGRA is allowed to mature until it takes (adheres) to the underlying tissue, which takes 2 to 4 weeks until the wound is amenable for split thickness skin grafting. Therefore, before consenting and enrollment into the study, the wound area to be studied will be treated first with INTEGRA™ MBWM then be allowed to heal for approximately two to four weeks (consistent with standard of care), at which time an assessment will be made to

determine if a viable granulation layer suitable for second stage grafting is present.
(Note: At this time the patient will complete the consent process as described below in Section 5.5.2).

The basic study design has the following characteristics:

- Each subject will serve as his/her own control
- After INTEGRA™ MBWM treatment (and once viable granulation is present), the study wound area will be divided into two regions within itself. Study treatment to each of the two regions will be assigned by randomization. Subjects will be blinded to treatment area assignments to avoid bias
- Each subject will be treated with meshed STSG over both the control and ReCell regions of the Integra-treated wound. The control area will have standard 1:1.5 meshing (only) STSG, and the experimental area will have 1:5 meshing STSG plus application of ReCell (ReCell will be applied over the 1:5 meshed STSG).

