6. ReCell suspension is then sprayed or dripped on wound followed by covering with recommended dressing

The surgeon will follow manufacturer instructions for determining the appropriate skin biopsy size to cover the ReCell treatment area. The ReCell donor site will be approximately 2cm x 2cm in area and harvested using a dermatome instrument of surgeon's choice set at a depth of 0.006 inch to 0.008 inch (equivalent to 0.15 - 0.2 mm) (Note: the thickness for traditional skin grafts are thicker at a depth of 0.012 inch to 0.016 inch). Selection of a site-specific donor site is important for promotion of the same functional and cosmetic characteristics as the area to be treated with ReCell; e.g., a donor site is chosen with similar pigment and texture to the treatment site. Site-specific characteristics may include the thickness of keratinocyte layers in glabrous tissues (soles of the feet and palms of the hands), melanocyte distribution and secretory functions of the epithelium. It is essential the donor site is clean, of appropriate depth, and shows no evidence of surrounding cellulitis or infection. Biopsy size, location and depth will be recorded in the eCRF.

For optimum cell viability, the skin sample should be processed immediately after harvesting. If a skin sample is harvested and processed according to the IFU, it should only require between 15 and 30 minutes of contact with the enzyme. The total time of incubation in enzyme solution will be recorded on the eCRF. Contact in excess of 60 minutes is not recommended by the manufacturer; if this should occur, a protocol deviation will be reported to the IRB and Medical Research Monitor.

The volume of suspension prepared is dictated by the size of the treatment area as identified in the ReCell IFU as indicated in the table below. The volume of cell suspension produced will be recorded on the eCRF.

Treatment Area	200 cm ² - 260 cm ²	>261 cm ² – 320 cm ²
Buffer Solution Volume	3 mL	4.5 mL

The cell suspension spray created using the ReCell device will be applied over the prepared STSG wound site meshed at 1:5 as detailed below. The PI and/or Co-PI (only) will apply the investigational product to the pre-determined wound region.

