Following surgery, subjects will be transferred to the Post Anesthesia Care Unit (PACU) and then to the In-Patient ward. Post-Operative recovery in terms of hospitalization and length of stay will be as per standard of care for this type of procedure.

It has been identified from previous use, the loss of formed skin at the ReCell site appears to be primarily associated with secondary trauma due to inadvertent inadequate care and/or protection of the newly epithelialized area. As a corrective measure, the wound will be appropriately protected while the skin is maturing. These measures include use of appropriate protective dressings after initial wound closure to give the epithelium adequate time to mature and cornify, ensuring the primary dressing removal is atraumatic and not before post-treatment Day 6 and avoidance of potentially damaging cleansing regimens and cytotoxic creams (i.e., silver sulfadiazine). Additionally, for the duration of their care, subjects will be informed on the following post-treatment ReCell site care

guidelines recommended by the manufacturer:

- Prevent the treated area from getting wet while the wound is still open
- Refrain from strenuous activity
- Protect the healed area; don't bump, wear loose clothing over treated area
- Once the area has healed, massage and keep area moisturized (using a gentle moisturizer) at least twice a day
- Avoid direct sun exposure at least 4 weeks following treatment and use sunscreen

Post-Treatment Study Visits

Subjects will be re-evaluated by the Orthopaedic Surgery Service, General Surgery Service and/or Plastic Surgery Service clinic at WRNMMC or on the in-patient wards. At all post-treatment study visits (Week 1 \pm 3 days, Weeks 2, 3, 4, 6 \pm 2 days, Weeks 12 and 24 \pm 14 days post-treatment), the PI and/or AI will perform the following assessments as outlined below:

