- **Allergic response to Enzyme (Trypsin):** The allergic response to Trypsin, the enzyme used in the ReCell Device for disaggregation of the biopsy, will be evaluated. An allergic response to Trypsin is most likely to present as contact dermatitis (defined as an altered state of skin reaction induced by exposure to an external agent). Substances that produce this condition after single or multiple exposures may be irritating or allergic in nature and induce an inflammatory response. The most common clinical expression of this induced inflammation is dermatitis (eczema). The evaluation tools for assessment of the allergic response to Trypsin have been developed in accordance with guidelines published in the Journal of the American Academy of Dermatology [Drake, LA, et al., 1995]. Any allergic response(s) to trypsin will be recorded in the eCRF and depending on severity, will have additional reporting to the IRB and Research Monitor.
- **Durability:** Abrasions or injuries at the graft site due to graft fragility will be noted and described in the eCRF.
- **Digital Photography:** The healing process at the ReCell donor site and at the treated and control wound sites will be documented pictorially. Photographs obtained will be documented in the eCRF.
- **Vital Signs:** Vital to be assessed include oral temperature, heart rate, respiratory rate and blood pressure. Results will be recorded in the eCRF.
- **Subject complaint:** Subject complaints will be rated on a 10-point scale by the subject utilizing the “patient” portion on the POSAS (*see description below*) for the treated wound sites and documented in the eCRF.
- **Adverse Events:** The research team will assess if the subject has experienced any adverse effects post-treatment with the investigational device. The subject will be asked if he/she has any problems, issues and/or concerns since the last encounter visit that could be potentially related to study participation. Other treatment-related adverse events requiring surgical intervention prior to Week 12 post-treatment and all serious adverse event (SAE) occurrences will be treated and recorded in the eCRF. For all adverse events, the Investigator will provide an assessment of the event, its treatment resolution, and relationship to the investigational device.

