5.7 Statistical Considerations

5.7.1 Study Endpoints

Primary Outcomes: Safety and Tolerability

The safety and tolerability endpoints for this feasibility clinical trial includes:

- Delayed healing/non-healing of wound and donor site
- Graft loss
- Heterotopic ossification
- Infection
- Scar contracture
- Durability (i.e. abrasions/injuries at graft site due to graft fragility)
- Allergic response to trypsin (the enzyme used in the ReCell process)
- Subject Complaint (i.e. pain and itching)
- Vital Signs
- Blood chemistries and hematology
- Treatment-related adverse events requiring surgical intervention prior to Week 12 post-treatment and all serious adverse event (SAE) occurrences throughout the study

Secondary Outcomes: Preliminary and Long-Term Efficacy

The preliminary efficacy (Week 1-6 post-treatment) endpoints for this feasibility clinical trial includes:

- Wound epithelialization 95% or greater re-epithelialization at treated wound site and donor sites
- Histology
- Patient pain rating

The long-term efficacy (Week 12 and 24 post-treatment) endpoints for this feasibility clinical trial includes:

- Scar assessment scale using the Patient and Observer Scar Assessment Scale (POSAS) and Vancouver Scar Scale
- Functional outcome rating
- Patient satisfaction
- Histology
- Radiographic evaluation for assessment of heterotopic ossification

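### Durability counts only breaks attributed to graft fragility, with no attribution rule and no stated blinding, so the ReCell-control comparison is open to differential attribution

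*Combined protocol and SAP*

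**What the plan says.** The visit instruction in section 5.5.4 (Post-Treatment Study Visits, Durability) reads: "Abrasions or injuries at the graft site due to graft fragility will be noted and described in the eCRF". The same causal qualifier appears wherever durability is defined: Specific Aim 1, the primary outcomes in 5.7.1, the by-treatment safety summary in 5.7.3, the risk list in 6.2 and schedule note l.

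On who judges, 5.5.4 says that at all post-treatment visits "the PI and/or AI will perform the following assessments as outlined below". On who knows the allocation, it says: "The PI and/or Co-PI (only) will apply the investigational product to the pre-determined wound region". Section 5.1 states: "Subjects will be blinded to treatment area assignments to avoid bias". Section 5.5.4 also blinds the two observers who score the POSAS and the Vancouver Scar Scale. No blinding is stated for the durability assessment.

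Under Post-Operative Care, 5.5.4 reports from previous use that "the loss of formed skin at the ReCell site appears to be primarily associated with secondary trauma due to inadvertent inadequate care and/or protection". Nothing similar is said about the control region.

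**The concern.** A graft's fragility shows itself when the skin gives way under a knock or rubbing. Fragility and minor trauma are therefore often two descriptions of one event, and the definition makes the assessor choose between them before the event counts. That choice is made without a rule and without stated blinding, and the protocol supplies a ready alternative cause for one of the two regions only. If the choice differs by region, the durability comparison shifts although the skin has not.

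The outcome matters to the study's own argument. Section 4.4 expects ReCell to improve healing in the mesh interstices, "thus improving durability among STSG gaps that are potential points of failure during later physical activity", and Specific Aim 3 makes durability of the regenerated tissue a focus of the long-term assessment. Breakage under mechanical load is what the study wants to observe, and it is also what the qualifier allows to be set aside. Section 5.7.2 says the results may be used to refine a pivotal trial.

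**Working it through.** **Figures in the plan.** None applies. Section 6.2 lists durability as a monitored risk but places it in none of its frequency bands, and 5.7.2 gives no formal sample size calculation. There is nothing to reproduce, and every rate below is an assumption.

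**What the text establishes.**

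1. An event needs a causal judgement to count (all six places listed above).
2. No criterion for that judgement is given, nor any instruction to record every break first and its cause second.
3. The assessor is the PI or AI. The PI or Co-PI applies ReCell, so a PI who treats and then assesses knows the allocation. Whether an AI knows it is not stated.
4. The trauma explanation is offered for the ReCell site only.

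**How far attribution can move the count.** Take n = 20 subjects (5.7.2), each with one ReCell and one control region.

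Counted rate = true rate × (1 − share put down to trauma).

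| Assumed true ReCell / control | Share called trauma, ReCell / control | Counted ReCell / control | True difference | Counted difference |
|---|---|---|---|---|
| 6/20 / 6/20 | 3 of 6 / 1 of 6 | 3/20 = 15% / 5/20 = 25% | 0 | −10 points |
| 6/20 / 6/20 | 1 of 6 / 3 of 6 | 5/20 = 25% / 3/20 = 15% | 0 | +10 points |
| 30% / 15% | 50% / 0% | 15% / 15% | +15 | 0 |
| 30% / 15% | 50% / 25% | 15% / 11.25% | +15 | +3.75 |
| 30% / 15% | 75% / 25% | 7.5% / 11.25% | +15 | −3.75 |
| 30% / 15% | 25% / 25% | 22.5% / 11.25% | +15 | +11.25 |

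With equal true rates of 20% to 40%, and 50–75% of ReCell events against 0–25% of control events called trauma, the false ReCell advantage runs from 5 points (20% × 0.50 = 10% against 20% × 0.75 = 15%) to 30 points (40% × 0.25 = 10% against 40% × 1 = 40%). Equal shares create no false difference when the true rates are equal, but they shrink a real one (last row). In the third row, three reclassified events remove a twofold excess.

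**Whether other records restore the comparison.**

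- *Graft loss and atypical healing* (5.5.4) carry no causal qualifier, but an abrasion after closure need not be graft loss. Delayed healing is defined by failure to reach 95% by Week 6.
- *Adverse events* are recorded whatever their relation to the device (6.2), but the tabulations in 5.7.3 are not specified by wound region. Each subject carries both treatments, so counts of subjects cannot give the contrast.
- *Photographs* are taken of both regions at each visit. Their only stated scoring is the 95% healing criterion, and they are labelled ReCell or control, so as written they are not a masked durability reading.

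**The case against.** The strongest reply is that nothing need be lost. Graft loss, atypical healing, adverse events and photographs are all collected, 5.7.3 promises listings of all data, and its by-treatment summary includes a general line for safety issues through 24 weeks. This stands against one tempting inference: that a break at the ReCell site enters the data only if it is blamed on fragility. The documents do not support that. The omission concerns the durability outcome, not the whole database. But the general safety line has no definition that would make it a durability count.

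A second reply is that the trauma remark explains why wounds are protected after surgery. It is not a scoring instruction, and damage to immature, poorly protected skin could itself be called fragility. This also stands. A reader might infer that investigators are told to score ReCell breaks as trauma; they are not. The remark shows only that the alternative cause is suggested for one region, and the text never says whether a break after minor trauma counts.

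Third, the two regions belong to one wound and receive the same dressings, so exposure to trauma should be similar. That limits a real difference in exposure. It does not limit a difference in how the same event is explained.

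Finally, the study is small and descriptive, and the sample eCRF and statistical management plan are present only as appendix titles. The form may already record all abrasions by region, which cannot be checked. The definition in the protocol would still need to agree with it.

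**Conclusion.** The point holds for the durability comparison. A listed primary safety outcome depends on an attribution made without a rule and without stated blinding, and the protocol suggests an alternative cause for one region only. Other records may retain an excluded event but do not rebuild the by-treatment durability contrast.

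The documents show that differential attribution is possible. They do not show that it occurs, in which direction, or how large it is. The illustration says only that, with 20 pairs, two or three reclassified events are enough to create, hide or reverse a difference of 10 to 15 points. It rests wholly on assumed breakdown rates and attribution shares. The point is worth correcting because the correction is cheap, although no formal hypothesis test depends on it.

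**What to change.** In 5.5.4, 5.7.1, 5.7.3 and schedule note l:

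- Record every abrasion, tear, blister or epithelial breakdown in region A and in region B at each visit, whatever the presumed cause.
- Put presumed cause (fragility, external trauma, other) in a separate eCRF field.
- Make the any-cause count by region, compared within subject, the main durability summary. Report the fragility-attributed count as descriptive.
- Do not restrict events to those after first closure. That would condition on a post-treatment outcome: a region that never closes could have no durability event, which could favour the side that heals worse. Show instead, beside the durability count, how many regions had reached 95% re-epithelialization, so that regions that never closed are not taken as durable.

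While note l is being edited, reconcile its visit schedule. The healing-assessment row appears to carry no mark at Week 24, while 5.5.4 places these assessments at every post-treatment visit.

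The cost is one definition and one eCRF field. Event counts rise in both regions and include some incidental injuries. If those injuries fall equally on the two regions, they add noise but leave the expected absolute difference unchanged. The change does not blind the assessor, who still decides whether a break is present, but that is a narrower judgement than deciding its cause.
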